6.2. Treatment Assessments

6.2.1. Week 4, 8, 16, 24, 32, 40 Assessments

The following evaluations will be performed at Weeks 4, 8, 16, 24, 32, and 40, unless otherwise specified. Study visits are to be completed \pm 4 days of the protocol-specified visit date, based on the Baseline Visit. Week 48 assessments are outlined in the following section (Section 6.2.2).

The following assessments and procedures will be performed and recorded on CRFs:

- Symptom-directed physical examination, including vital signs (complete physical examination including Tanner Staging at Week 24 only)
- Body weight and height

- Blood samples for:
 - Hematology (CBC with differential and platelet count)
 - Serum chemistry and liver function tests, including albumin, alkaline phosphatase, AST, ALT, total bilirubin (reflex to direct [conjugated] bilirubin if total bilirubin $> 1.5 \times$ ULN), bicarbonate, BUN, calcium, chloride, CPK, creatinine (and calculated creatinine clearance), glucose, LDH, magnesium, phosphorus, potassium, sodium, uric acid, and amylase (reflex lipase testing if total amylase is $\geq 1.5 \times$ ULN)
 - Hepatitis B serology (HBeAg and HBsAg; reflex HBeAb and HBsAb if Ag negative; Weeks 16 and 32 only)
 - Plasma HBV DNA (PCR method)
 - Plasma for determination of tenofovir concentration
 - Serum and plasma for storage (for potential pharmacokinetic and/or virologic assays, including resistance surveillance, HBsAg and HBeAg quantification and compliance assessment)
- Urine samples for:
 - Urinalysis (protein, glucose, blood)
 - At Week 24 only: urine biochemical markers (refer to Section 6.5. for details)
 - Urine pregnancy test (for females of childbearing potential only; positive urine pregnancy test will be immediately confirmed with a serum pregnancy test)
- At Week 24 only: dual energy x-ray absorptiometry (DEXA) scan of spine and whole body (DEXA scan must be performed ± 10 days from visit)
- Review of AEs and changes in concomitant medications
- Retrieval of study medication and assessment of medication adherence
- Study drug dispensing (including multivitamin) and instructions on appropriate dosing and administration
- At Weeks 4 and 24 only: Provide all subjects with a Subject Dosing Diary Card to complete the diary daily for 10 days prior to the next visit
- At Weeks 8 and 32 only: Collect the Subject Dosing Diary Card completed by the subject daily for 10 days prior to these visits

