7.3. Serious Adverse Events

A **serious adverse event** (SAE) is defined as follows:

Any adverse drug experience occurring at any dose that results in any of the following outcomes:

- Death
- Life-threatening situation. Life-threatening means that the subject was at immediate risk of death from the reaction as it occurred.

- In-patient hospitalization or prolongation of existing hospitalization (excluding those for study therapy or placement of an indwelling catheter, unless associated with other SAEs)
- Persistent or significant disability/incapacity
- Congenital anomaly/birth defect in the offspring of a subject who received study drug
- Other: medically significant events that may not be immediately life-threatening or result in death or hospitalization, but based upon appropriate medical and scientific judgment, may jeopardize the subject or may require medical or surgical intervention to prevent one of the outcomes listed above
- Examples of such events are as follows:
 - Intensive treatment in an emergency room or at home for allergic bronchospasm
 - Blood dyscrasias or convulsions that do not result in hospitalization
 - Development of drug dependency or drug abuse

For the purposes of this study, in addition to the above criteria, the following must be reported as SAE's:

- Serum ALT $> 2 \times$ baseline and $> 10 \times$ ULN, with or without associated symptoms.
- Confirmed ALT elevation (defined as 1-grade shift or $2 \times$ previous value) associated with confirmed changes outside of the normal range in other laboratory parameters suggestive of worsening hepatic function (abnormal PT ≥ 2 seconds or INR ≥ 0.5 over baseline, abnormal serum albumin ≥ 1 g/dL below baseline or elevated serum lactate levels (if available), defined as $2 \times$ ULN per the Adult AIDS Clinical Trials Group (AACTG) guidelines).
- Any clinical manifestations of hepatic decompensation (variceal bleeding, hepatic encephalopathy, or worsening of ascites requiring diuretics or paracentesis).

Clarification of Serious Adverse Events

- Death is an outcome; therefore, not an AE in itself; the SAE is the condition(s) that leads to death.
- The subject may not have been on study drug at the occurrence of the event. Dosing may have been given as treatment cycles or interrupted temporarily before the onset of the SAE, but may have contributed to the event.

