7.6.6. On-Treatment ALT Flare and Post-Treatment Exacerbation of Hepatitis Management

For subjects with bridging fibrosis or cirrhosis, study drug discontinuation with treatment-free follow-up is contraindicated due to the potential risk of exacerbation of hepatitis in the setting of low hepatic reserve which could lead to decompensation. Subjects with bridging fibrosis or cirrhosis should be placed on commercially available HBV therapy following study drug discontinuation.

On-Treatment ALT Flare and Post-Treatment Exacerbation of Hepatitis are defined as:

- Serum ALT $> 2 \times$ baseline and $> 10 \times$ ULN, with or without associated symptoms OR
- Confirmed ALT elevation (defined as 1-grade shift or $2 \times$ previous value) associated with confirmed changes outside of the normal range in other laboratory parameters suggestive of worsening hepatic function (abnormal PT ≥ 2 seconds or INR ≥ 0.5 over baseline, abnormal serum albumin $\geq 1 \text{ g/dL}$ below baseline or elevated serum lactate levels (if available), defined as $2 \times$ ULN per the Adult AIDS Clinical Trials Group (AACTG) guidelines).

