7.6.6.1. Management of ALT Flare in Subjects Receiving Study Medication

If laboratory results indicate (1) elevation of ALT $> 2 \times$ baseline and $> 10 \times$ ULN OR (2) abnormal laboratory parameters suggestive of worsening hepatic function (abnormal PT ≥ 2 sec above baseline, INR ≥ 0.5 above baseline, abnormal albumin ≥ 1 g/dL decrease from baseline or elevated serum lactate levels $> 2 \times$ ULN along with any ALT elevation (i.e., grade shift or $2 \times$ previous value), the following is recommended:

- Schedule the subject to return to the clinic as soon as possible and ideally no later than one week after the initial labs were drawn. During the visit, perform a clinical assessment of the subject. The assessment should include a physical examination and evaluation of the subject's mental status.
- Draw blood samples, request lactate testing and send for confirmation of elevated serum transaminases (ALT/AST), total bilirubin and PT/INR, and albumin. [Note: If, in the investigator's judgment, the central laboratory cannot provide adequate turn around time, the confirmation test may also be performed at a local laboratory. However, the central laboratory results are considered definitive].

If the elevations are confirmed, request the central clinical laboratory to conduct reflex testing for serum HBV DNA, HBV serology (HBeAg, HBeAb, and HBsAg), HDV, HAV IgM, and HCV serology.

Based on the results of the confirmatory tests, the following treatment modifications are recommended:

Elevated Liver Enzymes, Normal Bilirubin, Normal PT/INR, Normal Albumin, Normal Lactate

If ALT and/or AST levels are elevated (i.e., $> 2 \times$ baseline and $> 10 \times$ ULN) but total bilirubin and PT/INR, albumin and lactate are normal, the subject may remain on study medication and should be monitored every week until ALT/AST return to normal or baseline levels. During monitoring:

- If ALT/AST levels decline within 4 weeks, the subject should remain on study and return to the clinic per protocol.
- If after 4 weeks of monitoring, ALT/AST values remain elevated (e.g., $> 2 \times$ baseline and $> 10 \times$ ULN) or have worsened, with bilirubin $\leq 2.5 \times$ ULN, PT $\leq 1.5 \times$ ULN, or abnormal albumin or lactate levels, the investigator should consult with the Gilead Medical Monitor.

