7.6.6.2. Management of Exacerbation of Hepatitis in Subjects Who Have Discontinued Study Medication

If laboratory results indicate (1) an ALT elevation $> 2 \times$ baseline and $> 10 \times$ ULN OR (2) abnormal laboratory parameters suggestive of worsening hepatic function (abnormal PT ≥ 2 secs above baseline, abnormal albumin ≥ 1 g/dL below baseline or elevated lactate levels $> 2 \times$ ULN) along with any ALT elevation (i.e., 1 grade shift or $2 \times$ previous value) and the subject is on no post-study therapy for HBV, the following is recommended:

- Schedule the subject to return to the clinic as soon as possible and ideally no later than 1 week after the initial labs were drawn. During the visit, perform a clinical assessment of the subject. The assessment should include a physical examination and evaluation of the subject's mental status.
- Draw blood samples and request lactate testing and confirmation of elevated serum transaminases (ALT/AST), bilirubin, PT/INR, and albumin. [Note: If, in the investigator's judgment, the central lab cannot provide adequate turn around time, the confirmation test may also be performed at a local lab. However, the central lab results are considered definitive].

- If the elevations are confirmed (e.g., ALT > 2 × baseline and > 10 × ULN) OR (2) abnormal laboratory parameters suggestive of worsening hepatic function (abnormal PT ≥ 2 secs above baseline, abnormal albumin ≥ 1 g/dL below baseline, or elevated lactate levels > 2 × ULN) along with any ALT elevation (i.e., 1 grade shift or 2 × previous value), request the clinical laboratory to conduct reflex testing for serum HBV DNA, HBV serology (HBeAg, HBeAb, and HBsAg), HDV, HAV IgM and HCV. If serum HBV DNA is increasing, the investigator should consider immediate initiation of approved therapy.
- The subject should be followed until the abnormal ALT/AST values, PT/INR, albumin or lactate laboratory parameters return to normal or baseline up to a maximum of 6 months after the initial occurrence of the event. Refer to [Appendix 6](#) for specific guidelines for the management of symptomatic and asymptomatic hyperlactatemia.

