- g HBeAg and HBsAg and, if negative, reflex HBeAb and HBsAb, respectively.
- h Determination of HBV viral genotype (A–H) will be performed at the Baseline Visit for all subjects. Resistance surveillance will be conducted at Baseline for all subjects, and attempted for all viremic subjects (HBV DNA \geq 400 copies/mL [69 IU/mL]) at Weeks 48, 96, 144, and 192, as well as at the Early Discontinuation Visit, if applicable.
- i Including estimated creatinine clearance, by the Schwartz Formula (2 to <12 years old).
- j PT/INR will be performed at the Screening and Baseline Visits, then as a reflex test in subjects experiencing exacerbation of hepatitis thereafter.
- k For females of childbearing potential only; a serum β -HCG pregnancy test will be performed at Screening, Baseline, Weeks 48, 72, 192 and Early Study Drug Discontinuation/End of Treatment Visit (if applicable). Urine pregnancy testing will be performed at all other study visits through the end of the study including the Extension Phase. A positive urine pregnancy test must be confirmed immediately with a serum pregnancy test.
- l Blood (serum and plasma) collected for long-term storage and possible future testing (e.g., pharmacokinetic and/or virologic analysis).
- m DEXA scan will be performed between the Screening and Baseline Visits, and must be performed prior to randomization and receipt of study drugs. All other DEXA scans must be performed within \pm 10 days of the scheduled study visits. DEXA scan will be performed at the time of switch for subjects switching from placebo to tenofovir DF, unless the most recent DEXA scan was performed within 12 weeks earlier.
- n Specimens for bone biochemical markers must be collected in the morning in a fasted state, or, if fasting is not feasible, within two hours of the time of day that the Baseline Visit specimen was collected. For example, if the bone biochemical markers were drawn at 7:00 AM for the Baseline Visit, they must be drawn no earlier than 5:00 AM and no later than 9:00 AM for Week 24, 48, 72, 96, and subsequent specified visits. Bone biochemical markers will also be collected at the time of switch for subjects switching from placebo to tenofovir DF if not done within 12 weeks prior to switch. Bone biochemical markers will also be collected at the Screening Visit; the mean of the Screening and Baseline Visit values will constitute the study baseline, to which subsequent values will be compared.

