Appendix 3. Clinical Laboratory Assessments

Hematology:
 
Erythrocytes Hemoglobin Hematocrit Platelets Total leukocytes and differential (neutrophils, lymphocytes, monocytes, eosinophils, basophils)
	
Liver Tests:
 
Total bilirubin (reflex direct [conjugated] bilirubin) AST ALT Alkaline phosphatase Prothrombin time, INR Alpha-1 antitrypsin and protease inhibitor (PI) typing

Chemistry:
 
Creatine phosphokinase Lactic dehydrogenase (LDH) Creatinine and calculated creatinine clearance Albumin Glucose Serum amylase Lipase (if serum amylase is $\geq 1.5 \times$ ULN) α-fetoprotein (Screening Visit) Blood urea nitrogen (BUN) Uric acid Total iron (Screening Visit)
	
Urinalysis:
 
Protein Blood Glucose
 
Urine Pregnancy Test:
 
Post-menarchal females only (reflex serum β-HCG if positive)

Electrolytes:
 
Sodium Potassium Bicarbonate Phosphorus+ Calcium Magnesium Chloride
	
HBV Serology:
 
HBsAg, HBeAg (reflex HBsAb and HBeAb).

Bone Biochemical Markers:	
 urine bicarbonate and n-telopeptide; serum c-telopeptides, osteocalcin, bone-specific alkaline phosphatase, PTH, and vitamin D levels (25-hydroxy) and 1,25 (dihydroxyvitamin) D levels; fasting serum creatinine/phosphate and urine creatinine (spot)/phosphate for measurement of the renal phosphate threshold (TmP/GFR) 	Virology: Plasma and serum for HBV DNA and serology HIV, HAV, HDV and HCV (Screening Visit) Viral genotyping (A–H), resistance surveillance
	Tenofovir DF Concentration: Plasma concentration	
Serum β-HCG Pregnancy Test:	Post-menarchal females only; at Screening, Baseline, Weeks 48, 72, 192, or Early Study Discontinuation/End of Treatment Visits; reflex if urine test positive at all other study visits	Storage: Plasma and serum for storage

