7.2.3. ALT Flare and Exacerbation of Hepatitis

Summaries of the incidence of ALT flare and exacerbation of hepatitis will be provided by treatment group using the subjects in the Safety Analysis Set for on-treatment occurrences during the double-blind phase and off-treatment occurrences. On-treatment occurrences in the double-blind phase will be defined as occurrences in the period between the first dose of blinded study drug to the minimum of the last dose date of blinded study drug + 3 days and first dose date of open-label study drug, if applicable, for those who discontinued blinded study drug permanently. Off-treatment occurrences will be defined as occurrences after the last dose of study drug + 3 days. A supportive listing will also be generated.

Incidence of ALT flare and exacerbation of hepatitis is defined as:

- Serum ALT $> 2 \times$ study baseline and $> 10 \times$ ULN, with or without associated symptoms

OR

- Confirmed ALT elevation (defined as 1 grade shift [ie, increase] or $2 \times$ previous value) with confirmed changes outside of the normal range in other laboratory parameters suggestive of worsening hepatic function (abnormal prothrombin time ≥ 2 seconds over study baseline or international normalized ratio [INR] ≥ 0.5 over study baseline, and abnormal serum albumin ≥ 1 g/dL below study baseline or elevated serum lactate levels [if available], defined as $2 \times$ ULN).

If the first of two consecutive results is in the double-blind phase and the second is out of the double-blind phase (ie, in the open-label or TFFU phase), then the result will be considered to be confirmed in the double-blind phase (assuming both values meet the criterion). And if the criterion is met by the last value in the double-blind phase, and no assessments are available after due to the subject exiting the study or data not yet available (eg, due to the data-cut), then the result will also be considered to be confirmed.

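### SAP 7.2.3 joins the PT/INR and albumin/lactate criteria of the second ALT-flare limb with *and*, so an ALT rise with an albumin fall alone may go uncounted

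*SAP*

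**What the plan says.** SAP 7.2.3 counts an ALT flare or exacerbation of hepatitis through either of two limbs. The first is ALT above 2 x study baseline and above 10 x ULN. The second is a confirmed ALT elevation (one grade, or twice the previous value) with confirmed changes in other laboratory tests. In the list of those tests, PT and INR are joined by *or*, albumin and lactate are joined by *or*, and the two pairs are linked as follows: "over study baseline, and abnormal serum albumin".

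The protocol has the same two limbs, but its wording of the second differs from place to place:

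- Section 7.3 (events that must be reported as SAEs): "abnormal PT ≥ 2 seconds or INR ≥ 0.5 over baseline, abnormal serum albumin ≥ 1 g/dL below baseline or elevated serum lactate levels".
- Section 7.6.6 (flare definition), identical as far as it matters here: "abnormal PT ≥ 2 seconds or INR ≥ 0.5 over baseline, abnormal serum albumin", followed by albumin or lactate.
- Section 7.6.6.1 (management on study drug): "abnormal PT ≥ 2 sec above baseline, INR ≥ 0.5 above baseline, abnormal albumin ≥ 1 g/dL decrease from baseline or elevated serum lactate".
- Section 7.6.6.2 (management after study drug is stopped), without INR: "abnormal PT ≥ 2 secs above baseline, abnormal albumin ≥ 1 g/dL below baseline or elevated lactate levels".

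On measurement, protocol Appendix 2 says: "PT/INR will be performed at the Screening and Baseline Visits, then as a reflex test in subjects experiencing exacerbation of hepatitis thereafter". Albumin belongs to the chemistry panel drawn at every scheduled visit; Section 6.2.1 lists "Serum chemistry and liver function tests, including albumin, alkaline phosphatase" among others. Lactate is in neither the Appendix 2 schedule nor the Appendix 3 laboratory list, and SAP 7.2.3 uses it only if available.

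**The concern.** A programmer who codes the SAP sentence with *and* as a logical operator requires a PT/INR change as well as an albumin or lactate change, or some variant of that depending on the brackets assumed. A child with a confirmed ALT elevation and a confirmed albumin fall, but no PT/INR worsening and no lactate elevation, then drops out of the flare summary. The protocol's management lists treat that same picture as meeting the second limb.

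Two things are at stake. First, SAP 7.1.4 takes SAEs from the protocol's definition, so one event could appear in the SAE tables and be missing from the flare table of the same report. Second, the criterion most exposed to the *and* is the only one measured on schedule.

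**Working it through.** No sample size, rate or test enters this point. The check is a comparison of texts, followed by a truth table.

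**Step 1. The texts side by side, taking the ALT elevation as confirmed.**

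| Place | Link between PT/INR and albumin/lactate | Albumin fall alone qualifies? |
|---|---|---|
| Protocol 7.3 and 7.6.6 | comma only | not settled by the sentence itself |
| Protocol 7.6.6.1 | one list of four, closed by *or* | yes |
| Protocol 7.6.6.2 | one list of three (no INR), closed by *or* | yes |
| SAP 7.2.3 | *and* | depends on the reading; see Step 2 |

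The comma in 7.3 and 7.6.6 does not decide the matter. Sections 7.6.6.1 and 7.6.6.2 stand under the same heading and restate the limb as alternatives. Read together, the protocol treats an albumin fall as sufficient alongside the ALT elevation.

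**Step 2. The possible readings of the SAP sentence.** Write P, I, A and L for the PT, INR, albumin and lactate criteria. The sentence has the form P or I and A or L, which has four logically distinct bracketings:

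| Reading | Albumin alone (A true, the rest false) |
|---|---|
| (P or I) and (A or L) | rejected: P or I is false |
| ((P or I) and A) or L | rejected: P or I is false and L is false |
| P or (I and (A or L)) | rejected: P is false and I is false |
| P or (I and A) or L | rejected: P, I and L are all false |
| *and* as a loose list connector: P or I or A or L | accepted |

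All four conjunctive readings reject albumin alone. Only the list-connector reading agrees with 7.6.6.1. INR alone is also rejected by all four, but the protocol is not uniform there because 7.6.6.2 omits INR. Albumin alone is therefore the clean case.

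**Step 3. What is measured, and when.** The double-blind phase has 7 scheduled post-baseline visits to Week 48 (Weeks 4, 8, 16, 24, 32, 40, 48). Albumin is scheduled at 7 of 7, PT/INR at 0 of 7 and lactate at 0 of 7. For subjects kept blinded to Week 72 the figures are 10 of 10, 0 of 10 and 0 of 10. After Baseline, PT/INR can arise in three ways:

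- at the recall visit recommended in 7.6.6.1 and 7.6.6.2;
- during the weekly flare monitoring in 7.6.6.1, which implies repeat PT/INR;
- as a reflex test at treatment-free follow-up visits (6.3.1 and Appendix 2).

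Under the first bracketing in Step 2, the limb cannot be met at all if PT/INR was not drawn.

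**Step 4. Whether the second limb matters when the first exists.** Entry requires ALT of at least 1.5 x ULN, which is Grade 1 on the protocol's scale. From that floor a one-grade shift begins above 2.5 x ULN, while the first limb needs more than 10 x ULN. The second limb therefore covers events that the first does not.

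**The case against.** The strongest objection is that the any-of comparator is inferred. The controlling texts are the SAE rule and the flare definition, and both are silent at the critical comma. Sections 7.6.6.1 and 7.6.6.2 are triggers for recalling a subject on unconfirmed results. A recall trigger can reasonably be wider than a confirmed definition, and the two lists do not even agree on INR. This stands as a limit: a reader might infer that the protocol plainly defines a flare by any one criterion, and 7.3 and 7.6.6 on their own do not say that. It does not rescue the SAP sentence, which adds a connector found in none of the four protocol statements.

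A second objection concerns missing data. A reader might infer from the visit schedule that PT/INR will usually be absent. The documents do not support that. The recall visit draws ALT, bilirubin, PT/INR, albumin and lactate together, and there are the other reflex routes. What remains is an isolated albumin fall with PT/INR either not worsened or not drawn.

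A third objection is that little information is lost. ALT grade shifts, and an albumin fall below the normal range from a normal baseline, appear in the treatment-emergent laboratory abnormality table. SAEs are identified by the protocol's rules and tabulated separately. This is correct. What can be lost is the joint label in the flare summary and listing.

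Finally, a reader might infer that the SAP departs silently from a protocol-specified analysis because SAP 7.11 does not mention flares. Protocol 8.9 specifies no flare analysis, so that inference fails and the point does not rest on it.

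**Conclusion.** The point holds in a limited form. SAP 7.2.3 inserts *and* where the protocol has a comma or an *or*-list, and every conjunctive reading rejects an ALT elevation with an albumin fall alone. Coded that way, the rule may undercount flares.

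Its size is small and cannot be computed. The number of affected events is unknown and may be zero. A reader might want to use the number of criterion patterns that each reading accepts as a magnitude. That would be wrong: these are logical patterns and not events, and PT and INR are not independent measurements.

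The effect is confined to one descriptive summary and its listing. The first limb, the SAE tables and all efficacy analyses are untouched, so it would also be too strong to say that SAEs would go unreported.

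Confidence is high that the SAP adds the word and that albumin alone then fails. It is moderate that 7.3 and 7.6.6 mean any one criterion, because that rests on reading them with 7.6.6.1 and 7.6.6.2. The point still merits correction, because a safety definition that can be coded in several ways is not adequately pre-specified and the cost of repair is trivial.

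**What to change.** Reconcile SAP 7.2.3 with protocol 7.3 and 7.6.6 so that the flare table uses the protocol's definition. Read together as now written, that means replacing *and* with *or*: a confirmed ALT elevation plus at least one listed criterion, with a missing component not blocking the others.

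If a narrower analysis definition is intended, bracket it so that it has one reading, and state in the SAP that it differs from the protocol and why.

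The protocol's own statements should be reconciled at the same time: the comma in 7.3 and 7.6.6, the four-item list in 7.6.6.1, and the list without INR in 7.6.6.2. This review takes no position on which list is clinically right.

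The cost in the SAP is one word or one pair of brackets, plus a programming check. No new data are needed.

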6.3. Post-Treatment/Treatment-Free Follow-up Assessments

6.3.1. Follow-Up Assessments

For subjects with known bridging fibrosis or cirrhosis, study drug discontinuation with treatment-free follow-up is contraindicated due to the potential risk of exacerbation of hepatitis in the setting of low hepatic reserve which could lead to decompensation. Subjects with bridging fibrosis or cirrhosis should be placed on commercially available HBV therapy following study drug discontinuation.

Subjects who have received at least one dose of study drug and permanently discontinue study drug will be followed for 24 weeks off treatment or up to initiation of active treatment, whichever occurs first. The treatment-free follow-up period could occur for early discontinuation subjects or at Week 192 study completion.

For those subjects who remain off treatment, the following evaluations are to be completed every 4 weeks through the Week 24 Follow-Up Visit (Follow-Up Weeks 4, 8, 12, 16, 20 and 24). Each follow up visit should be conducted within ± 3 days from the protocol-specified visit date, calculated from the date of last dose.

- Symptom-directed physical examination, including vital signs
- Body weight and height
- Blood samples for:
 - Serum chemistry and liver function tests, including albumin, alkaline phosphatase, AST, ALT, total bilirubin (reflex to direct [conjugated] bilirubin if total bilirubin $> 1.5 \times$ ULN), bicarbonate, BUN, calcium, chloride, CPK, creatinine (and calculated creatinine clearance), glucose, LDH, magnesium, phosphorus, potassium, sodium, uric acid, and amylase (reflex lipase testing if total amylase is $\geq 1.5 \times$ ULN)
 - Hepatitis B serology (HBeAg and HBsAg; reflex HBeAb and HBsAb if Ag negative) (Follow-Up Week 24 only)
 - Plasma HBV DNA (PCR method)
 - Serum and plasma for storage (for potential pharmacokinetic and/or virologic assays, including resistance surveillance, HBsAg and HBeAg quantification and compliance assessment)
 - Prothrombin time (PT), international normalized ratio (INR) (reflex test in case of post-treatment exacerbation of hepatitis)
- Review of AEs and concomitant medications

Subjects experiencing post-treatment exacerbation of hepatitis during the 24-week post-treatment period should be followed weekly until their ALT levels return to Grade 2 or baseline, as described in the Toxicity Management section of the protocol (Section 7.6.)

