7.1.4. Serious Adverse Events

Serious adverse events (SAEs) will be identified and captured as SAEs if the AEs met the definitions of SAEs that were specified in the study protocol. SAEs captured and stored in the clinical database will be reconciled with the SAE database from the Gilead Drug Safety and Public Health Department before data finalization.

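### SAP 7.2.3 joins PT/INR to albumin or lactate with *and* where the protocol lists alternatives, so some protocol-defined ALT flares drop out of the flare summary

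*SAP*

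**What the plan says.** Protocol 7.6.6 sets the definition, introduced by "On-Treatment ALT Flare and Post-Treatment Exacerbation of Hepatitis are defined as". It has two criteria. The first is serum ALT above 2 × baseline and above 10 × ULN. The second is a confirmed ALT elevation (a one-grade shift or twice the previous value) together with a confirmed change in another marker of hepatic function. Those markers form a comma list closed by *or*. The same list is in the study-specific SAE rule in protocol 7.3: "abnormal PT ≥ 2 seconds or INR ≥ 0.5 over baseline, abnormal serum albumin ≥ 1 g/dL below baseline or elevated serum lactate levels".

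The two management sections use the same structure. Protocol 7.6.6.1 (on study drug) has "INR ≥ 0.5 above baseline, abnormal albumin ≥ 1 g/dL decrease from baseline or elevated serum lactate levels". Protocol 7.6.6.2 (off study drug) has "abnormal PT ≥ 2 secs above baseline, abnormal albumin ≥ 1 g/dL below baseline or elevated lactate levels"; it gives a PT threshold but none for INR. None of the four places has *and* between these markers.

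SAP 7.2.3 defines the event for the by-arm summary and supportive listing, on treatment in the double-blind phase and off treatment. Its first criterion matches the protocol. Its second keeps *or* between PT and INR, then continues "over study baseline, and abnormal serum albumin ≥ 1 g/dL below study baseline or elevated serum lactate levels".

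SAP 7.11 records three changes to the protocol's safety analyses: the baseline for BMD and bone markers, the treatment-emergent window, and the test for percent change in spine BMD. The flare definition is not among them.

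**The concern.** Two documents define an event of the same name by different rules, and the analysis rule is narrower. The protocol's list decides what investigators report as an SAE. ALT flare is also one of the situations in which protocol 5.1 releases serial HBV DNA values to the investigator during the blinded phase. A programmer who follows SAP 7.2.3 literally would then leave some of those children out of the flare table. The report would show flares as SAEs that the flare summary does not contain, and the by-arm incidence would be too low for a hepatic safety outcome of direct interest in a placebo-controlled hepatitis B trial.

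**Working it through.** The SAP states no figure for this rule, so there is nothing to reproduce. The check is a comparison of the two rules.

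**Inputs.** Take a confirmed ALT elevation that does not meet the first criterion. Let P = qualifying PT or INR change, A = qualifying albumin fall, L = qualifying lactate elevation.

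- Protocol 7.6.6 and 7.3: P or A or L.
- SAP 7.2.3, reading 1: P and (A or L). This is the reading the comma best supports.
- SAP 7.2.3, reading 2: (P and A) or L.

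**All seven patterns with at least one abnormality:**

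| Abnormal | Protocol | SAP reading 1 | SAP reading 2 |
|---|---|---|---|
| P only | counted | omitted | omitted |
| A only | counted | omitted | omitted |
| L only | counted | omitted | counted |
| P + A | counted | counted | counted |
| P + L | counted | counted | counted |
| A + L | counted | omitted | counted |
| P + A + L | counted | counted | counted |
| **Total** | **7** | **3** | **5** |

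Albumin alone and PT/INR alone are omitted under both readings.

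**Lactate normal or not available.** The possible patterns are P, A and P + A. The protocol counts 3; the SAP counts 1 (P + A) under either reading.

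**A third parse.** If the comma is ignored and PT and INR are treated as separate flags, the SAP sentence could be parsed as PT or (INR and albumin) or lactate. With four flags there are 16 combinations. The protocol counts 15 (all but the empty one). The SAP counts:

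- reading 1: 3 × 3 = 9
- reading 2: 8 + 3 = 11
- third parse: 8 + 5 = 13

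With lactate not available (8 combinations) the counts are protocol 7 and SAP 3, 3 and 5. PT alone is counted under the third parse. INR alone and albumin alone are omitted under all three.

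**What this means for one child.** ALT rises by one grade and is confirmed, without exceeding 10 × ULN. Albumin is confirmed abnormal and at least 1 g/dL below baseline. PT/INR is normal, and lactate is normal or not measured. Protocol 7.6.6 calls this a flare and protocol 7.3 makes it an SAE. SAP 7.2.3 does not count it under any of the three readings.

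**The case against.** The strongest reply is that little is lost.

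- Under SAP 7.1.4, events are "captured as SAEs if the AEs met the definitions of SAEs that were specified in the study protocol", so an omitted flare should still appear in the by-arm SAE summary and the SAE listing.
- ALT, albumin, PT and INR are all graded in protocol Appendix 4, and treatment-emergent abnormalities are summarised by arm (SAP 7.2.2.1 and 7.2.2.3).
- ALT above 2 × baseline and above 10 × ULN is caught by the first criterion, so only smaller rises are affected.
- No hypothesis test uses the table, and the same rule applies in both arms.

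All of this stands and limits the point to minor severity. It does not restore the missing count. In children under 16, albumin from 2.0 g/dL to below the lower limit of normal is Grade 2, which is outside the Grade 3 or 4 listing. The separate summaries also do not link an albumin fall to an ALT rise in the same child.

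A second reply is that *and* was only a list word. That is plausible, and the silence of SAP 7.11 suggests a drafting slip rather than a decision. The sentence still needs the same correction, because a programmer can follow it literally.

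A reader might go further and infer that the second criterion cannot be ascertained because PT/INR is not scheduled on treatment. Protocol Appendix 2 says "PT/INR will be performed at the Screening and Baseline Visits, then as a reflex test in subjects experiencing exacerbation of hepatitis thereafter", and 6.3.1 likewise makes it a "reflex test in case of post-treatment exacerbation of hepatitis". The documents do not make this an error. Children with decompensated disease are excluded (4.3). Albumin is measured at scheduled visits, and an abnormal albumin with an ALT elevation brings a PT/INR draw under 7.6.6.1. Abnormal findings are to be investigated for etiology (7.6), and clinical decompensation is an SAE in its own right (7.3). Reflex-only PT/INR is a reasonable choice in children aged 2 to under 12.

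**Conclusion.** The concern holds: SAP 7.2.3 is wrong as written, with minor severity. Its second flare criterion is narrower than the protocol's, and the difference is not declared. Read with the comma, it omits a confirmed ALT elevation accompanied by an albumin fall alone or by a PT/INR change alone. When lactate is normal or unavailable, it requires both a PT/INR change and an albumin fall.

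The size is known only as patterns. The seven patterns are not equally likely, and the documents give no rates from which to estimate how many children would be affected, or whether the arms would differ. The direction is known: the SAP can only count the same number of flares as the protocol, or fewer.

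A reader might infer that SAEs go unreported or that an efficacy conclusion is at risk. Neither follows. SAE capture uses the protocol definition, and the flare table feeds no efficacy endpoint. The conclusion assumes that the SAP sentence is programmed as punctuated and that protocol 7.6.6 is the intended definition; nothing in either document shows that a narrower one was wanted.

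**What to change.** In SAP 7.2.3, change *and* to *or* before the albumin criterion, so that PT/INR, albumin and lactate are alternatives as in protocol 7.6.6. The cost is one word and the matching line of program code. No new data, visits or protocol amendment are needed. The flare count may rise slightly and would then agree with the protocol-defined SAEs. If the narrower rule was in fact intended, it should be declared in SAP 7.11 with a reason.
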